a Every 12th week from the start of the ITI treatment period.

b Vital signs include blood pressure, pulse rate, respiratory rate, and temperature. Postdose assessments following rFVIIIFc injections should be taken approximately 20 minutes after the end of the injection.

c Sample to be used to determine seropositivity, including anti-HIV-1 and -2, anti-HBs, and anti-HCV, at screening, should patients be diagnosed with HIV, hepatitis B, or hepatitis C, and results not already available in medical records.

d Not mandatory. To be collected at the baseline visit or at later visits unless results are available in medical records.

e Patients will be instructed that they will receive their daily dose of rFVIIIfc during the study visit after the samples for inhibitor testing and the FVIII:C pre-dose assessment are taken.

f A whole blood sample will be collected at the baseline visit (predose) and at Week 2, as allowable based on patient weight, regulatory guidelines and institutional practice regarding blood draw restrictions for pediatric patients.

g A pre-dose sample for FVIII:C will be collected at visits where samples for IR or t½ assessments are not collected.

h Assessment of incremental recovery will only be performed after negative inhibitor has been confirmed at two consecutive visits.

i Half-life determination will only be performed after incremental recovery >66% of the expected IR has been confirmed at two consecutive visits. Half-life determinations are to be performed after at least a 24-hour washout.

j It is recommended that patients/caregivers enter dosing information immediately after an injection.

**Table 2** Schedule of events: Tapering and follow-up period

Activities	Tapering period	Follow-up period		Final safety follow-up
	Tapering initiation visit, Week 2, 4, 8, 12 and 16 visits	Week 28 and 40 visits	End of treatment visita	Final safety follow-up visit
	Starting at ITI success and continuing for 16 weeks with visits after 2 weeks ( $\pm 3$ days), 4 weeks ( $\pm 1$ week) and then every 4 th week ( $\pm 1$ week)	Visits week 28 and 40 ( $\pm 2$ weeks) following ITI Success	Visit week 48 ( $\pm 2$ weeks) following ITI Success OR 2 weeks ( $\pm 3$ days) after failure or 60 weeks of treatment	7 to 14 days after the last dose of rFVIIIfc

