### **9.3.4 Analysis related to secondary objective**

#### **9.3.4.1 Time to ITI success**

Time to ITI success will be analyzed descriptively using Kaplan-Meier estimates including median, 25th and 75th quartile. A Kaplan-Meier plot will be generated. Patients not achieving ITI success during the up to 60 weeks ITI period will be censored at the last observed time for this analysis. The ITIFAS analysis set will be used for this analysis.

Time to ITI success will also be summarized descriptively for the patients achieving ITI success.

Time to confirmed negative titer will be analyzed in the similar way.

Time to confirmed Incremental recovery >66% of the expected IR will be analyzed similarly as well on the subset of patients who reached confirmed negative titer.

For the subset of patients who were classified as partial success at the end of the ITI period, the time to fulfillment of the criteria for partial success will also be analyzed descriptively.

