**6.2.1 *ITI Full Analysis Set***

The ITI full analysis set (ITIFAS) will include all patients receiving at least one dose of rFVIIIFc and will be used for describing efficacy and safety during ITI treatment.

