### **6.3.13 Analysis Related to the Secondary Objectives**

#### **6.3.13.1 Time to ITI Success**

Time to ITI success in weeks will be analysed with descriptive summary statistics. The same will be done for patients achieving confirmed negative titer, confirmed incremental recovery  $> 66\%$  of the expected IR and the time until terminal half-life criteria is met respectively. For the descriptive analysis, the time for a patient who either never reaches the criteria or for whom the criteria are never assessed due to not fulfilling the required condition will be considered to be missing.

Time [week] to ITI success will also be analysed descriptively using Kaplan-Meier estimates including median, 25th and 75th quantile. It is considered likely that it will not be possible to provide estimates for the median and the quantiles, due to the success rate not being high enough and the proportion of censored data being too high. Each subsequent week then starts on the seventh day after the first day of the previous week.

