**PAREXEL International**  
**Statistical Analysis Plan**

Patients who do not achieve ITI success will be treated as follows:

- Patients who discontinued because there was no downward trend of 20% in titers will be considered censored at the time of treatment failure.
- Other patients are considered to be censored at the last observed time. This includes patients who withdrew due to safety concerns or who did not achieve the criteria for ITI success within 60 weeks of starting ITI with rFVIIIFc.

A Kaplan-Meier plot of the cumulative probability of success function will be generated by using the PROC LIFETEST in SAS software.

The following code (or similar code) will be used:

```
PROC LIFETEST DATA = iti_success PLOTS = SURVIVAL;
  TIME success_time * censored (1);
RUN;
```

The same analysis will also be done for the following:

- Time to confirmed negative titer
- Time to confirmed incremental recovery >66% of the expected IR

The ITIFAS analysis set will be used for this analysis. Week for the purpose of this analysis will be defined as follows: the study day/7, rounded up.

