## 9. FIGURES

**Figure 14.2.1.1** Kaplan-Meier Plot for Time to ITI Success (ITIFAS)

**Figure 14.2.1.2** Kaplan-Meier Plot for Time to Confirmed Negative Titer (ITIFAS)

**Figure 14.2.1.3** Kaplan-Meier Plot for Time to Confirmed Incremental Recovery Greater than 66% of the Expected (ITIFAS)

**Figure 14.2.1.4** Number and Percentage of Patients with each ITI Outcome versus Time (ITIFAS)

**Figure 14.2.3.1** Spaghetti Plot of Weekly Dose (IU/kg) versus Time During Tapering Period (TPFAS)

**Figure 14.2.4.1** Individual Inhibitor Titer Profiles in Linear and Semi-logarithmic Scale (ITIFAS)

**Figure 14.2.4.2** Mean ( $\pm$  Standard Deviation) Inhibitor Titers versus Nominal Time in Linear and Semi-logarithmic Scale (ITIFAS)

**Figure 14.2.6.1** Individual Local Laboratory FVIII:C Concentrations versus Study Day (ITIFAS)

PAREXEL International  
Statistical Analysis Plan

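### Time to confirmed IR >66%: the protocol analyses the confirmed-negative subset, the SAP analyses all ITIFAS patients, and the change is not recorded

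*SAP*

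**What the plan says.** Protocol 9.3.4.1 assigns ITIFAS to time to ITI success. It then says that time to confirmed IR above 66% of expected "will be analyzed similarly as well on the subset of patients who reached confirmed negative titer". It gives no time origin for that subset analysis.

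SAP 6.3.13.1 says that the analysis used for time to ITI success is repeated for time to confirmed negative titer and for time to confirmed IR >66%, and closes with "The ITIFAS analysis set will be used for this analysis". That sentence is generic, but the output list leaves no doubt: Table 14.2.1.6 and Figure 14.2.1.3 are both labelled ITIFAS. SAP 6.2.1 says this set "will include all patients receiving at least one dose of rFVIIIFc". The SAP counts weeks from study day, so its clock starts at first dose.

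Three other provisions bear on the point:

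- Protocol 7.5.1.1, Table 1 footnote: "Assessment of incremental recovery will only be performed after negative inhibitor has been confirmed at two consecutive visits".
- SAP 6.3.13.1, descriptive summary only: the time for a patient whose criteria are "never assessed due to not fulfilling the required condition will be considered to be missing". No such rule is given for the Kaplan-Meier analysis.
- SAP 6.3.13.1, Kaplan-Meier: patients stopped for lack of a downward titer trend "will be considered censored at the time of treatment failure".

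**The concern.** The protocol named a population for this analysis and the SAP replaced it without comment. The SAP's introduction says that it supplies details the protocol does not provide, but here the protocol did provide one. Following the SAP drops a protocol-specified analysis.

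The replacement matters because confirmed negativity is the gate to IR assessment. On the subset, the curve describes how many patients recover, and how fast, once the inhibitor is gone. On ITIFAS it mixes the chance of becoming negative with the chance of recovering afterwards.

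The ITIFAS curve has a further difficulty. Kaplan-Meier treats a censored patient as someone who could still have the event at the rate of those remaining. A no-trend failure has left ITI with a positive inhibitor and will not contribute a confirmed IR event. Censoring that patient therefore pushes the later part of the curve above the share of treated patients who actually recover.

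The protocol's wording also needs completing. Membership of the subset is decided after ITI start. If the clock starts at first dose, which is one reading of the protocol's wording, every member has a stretch of time in which no event is possible.

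**Working it through.** The plan states no expected IR rate or curve, so there is no figure of its own to reproduce. What follows is illustration under stated assumptions.

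**Inputs**

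- Planned N = 20 (Protocol 9.1).
- Rescue-ITI chart review in Protocol 5.1.2: 12 patients, 7 negative, 3 of those with normal recovery, at weeks 3, 14 and 65. Time to negative ranged up to 67.6 weeks.
- Earliest no-trend failure about week 36, from the minimum duration in Protocol 7.1 (4 + 36 + 2 = 42 weeks).
- Assumption: the review's negative titer and normal recovery stand in for this trial's confirmed criteria.

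**Step 1. Crude proportions**

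- All three recoveries counted: subset 3/7 = 42.9%; all treated 3/12 = 25.0%.
- Week-65 recovery excluded, since it falls outside the 60-week ITI period: subset 2/7 = 28.6%; all treated 2/12 = 16.7%.
- The patient who turned negative at week 67.6 also removed from the subset: 2/6 = 33.3%.

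**Step 2. Effect of censoring failures**

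Take N = 20 with 12 negative (20 × 7/12 = 11.7) and 5 IR events (20 × 3/12). The subset curve ends at 5/12 = 41.7%, and the true share of treated patients recovering is 5/20 = 25.0%. Suppose the 8 never-negative patients are censored together part-way through, with k of the 5 events after that point. The number at risk afterwards is 20 − (5 − k) − 8 = 7 + k, so the ITIFAS curve ends at

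1 − [(15 + k)/20] × [7/(7 + k)].

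| Events after censoring (k) | ITIFAS end value |
|---|---|
| 0 | 25.0% |
| 1 | 1 − 0.80 × 7/8 = 30.0% |
| 2 | 1 − 0.85 × 7/9 = 33.9% |
| 3 | 1 − 0.90 × 7/10 = 37.0% |
| 4 | 1 − 0.95 × 7/11 = 39.5% |
| 5 | 1 − 7/12 = 41.7% |

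If the same 8 patients stay at risk to week 60, the value is 25.0% whatever k is. With identical recoveries, the ITIFAS curve can thus end anywhere from the true share up to the subset value.

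**Step 3. Simulation with the 60-week limit enforced**

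There were 4,000 trials of 20 patients. P(negative) was 7/12. Time to negative was lognormal with median 14.1 weeks (from the chart review) and an assumed sigma of 0.8. Recovery came 6 to 12 weeks later (assumed). Never-negative patients were censored at week 36 with probability 0, 0.5 or 1, and otherwise at week 60.

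| P(IR given negative) | Subset, mean end value | ITIFAS, mean end value |
|---|---|---|
| 3/7 | 0.42 | 0.24, 0.25, 0.28 |
| 2/7 | 0.28 | 0.16 to 0.18 |

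The gap is 10 to 18 points (0.28 − 0.18 to 0.42 − 0.24). At 3/7 a median was estimable in about 35% of subset runs and 1-5% of ITIFAS runs. The true share of treated patients recovering by week 60 at 3/7 was 0.24, so censoring every never-negative patient at week 36 inflated the ITIFAS estimate by about 4 points.

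**The case against.** The case for leaving the plan alone has real content.

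- Time to confirmed IR is not among the listed endpoints in Protocol 6.2.1, and the study is descriptive, with no tests or confidence intervals.
- Protocol 9.3.1 leaves the detailed description of analyses to the SAP, and the SAP's text, table and figure all say ITIFAS. A reader might infer that programmers face contradictory instructions. They do not; the fault is an unrecorded departure from the protocol.
- SAP 6.3.12.1 already counts patients meeting each success criterion and lists the study day each was met, so a crude recovery proportion among negative patients can be derived. It does not give the time curve that the protocol asked for.

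Two further inferences go beyond the documents. The first is that never-negative patients are never tested for IR. Protocol 7.5.1.5.2 draws pre- and post-dose IR samples at the end of treatment visit, which failures also attend. What stands is narrower: one such sample cannot satisfy a criterion that needs two consecutive visits.

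The second is that this trial's curve will end at 43% or at 25-31%. Those percentages rest on an external chart review that is not a planning value, and they count a recovery at week 65. Nor is 31% a ceiling, as the table in step 2 shows.

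The gap is about one standard error of the subset estimate (0.15 at 3/7). That does not dismiss it, because both curves come from the same trial and the difference lies in what is estimated.

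**Conclusion.** The conflict stands on the text alone: two populations for one Kaplan-Meier analysis, with no record of the change. The two versions estimate different quantities. The ITIFAS version, with no-trend failures censored at failure, should not be read as the proportion of treated patients who recover, because it overstates that proportion whenever IR events follow those failures.

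The size is illustrative. It rests on the chart review's rates (7/12 negative, 2/7 to 3/7 of those recovering), on those outcomes matching the trial's confirmed criteria, on the assumed timing, and on a 60-week limit. The curve then ends near 28-42% on the subset and near 16-28% on ITIFAS. The ITIFAS value approaches the subset value if failures are censored before the IR events.

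This is a supportive analysis under the secondary time-to-success endpoint. It should be corrected, but it does not touch the primary proportion.

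**What to change.** In SAP 6.3.13.1, Table 14.2.1.6 and Figure 14.2.1.3:

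1. Restore the analysis of time to confirmed IR >66% on patients with a confirmed negative titer.
2. State its time origin. The date of confirmed negative titer is preferable, because membership is decided after ITI start. Say which of the two negative visits supplies that date.
3. Record this as a clarification of, or change to, Protocol 9.3.4.1. The protocol states no origin for the subset, so a clock from negativity should not be presented as the protocol analysis simply carried over.
4. If the ITIFAS version is also kept, label it separately as recovery among all treated patients. Keep treatment failures and other never-negative completers in the risk set to week 60, or use cumulative incidence, in place of censoring at failure.

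The cost is SAP wording and one extra table and figure, with no new data. The subset estimate will be imprecise, with roughly 12 patients under the assumed rate, and patients who turn negative late will have little time left before week 60.

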### 7.1.2 ITI period

The first dose of rFVIIIFc will be administered at the baseline visit and the ITI treatment will continue until ITI success or failure is declared, or for a maximum of 60 weeks. The ITI regimen

consists of daily administration of rFVIIIFc (200 IU/kg per day), which may be given as once daily injection or divided in two injections per day at the discretion of the investigator.

Visits will occur 2 and 4 weeks after the baseline visit and then every 4th week. For patients who achieves an IR >66% of the expected IR for each specific patient as per investigator judgment, the visit frequency will be changed to every other week.

During the ITI period patients will undergo procedures and assessments as per the schedule of events (Table 1). Samples for inhibitor testing and assessment of FVIII:C levels will be analyzed at the local laboratory as well as centrally. The results from the local laboratory will constitute the primary data of the study to be used for statistical analysis.

At each visit the inhibitor titer will be assessed. If, after the initial 3 months, a downward trend of at least 20% in the inhibitor titer in any 6-month period is not seen, the patients should be regarded as a treatment failure and complete the end of treatment visit as soon as possible.

The assessment of ITI outcome is illustrated in Figure 2. Once a patient has demonstrated negative inhibitor (<0.6 BU/mL) at two consecutive visits, evaluation of IR will be performed at the next visit. When an IR >66% of the expected IR has been obtained at 2 consecutive visits, pharmacokinetic assessments to determine half-life will be performed at the subsequent visits until a half-life of  $\geq 7$  hours is attained. Patients are required to have at least a 24-hour washout prior to the half-life assessment.

An unscheduled visit after the 60-week period may be scheduled to allow the patient to get a confirmatory test, as long as the first test occurred during the 60-week period. If the second test confirms the results of the first test, the date of ITI outcome is the date of the first value, which occurred during the 60-week period. Fluctuations in inhibitor levels is common and variability in inhibitor titer is expected. Patients will be evaluated on a case-by-case basis.

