## PAREXEL International

### Statistical Analysis Plan

- Kit numbers of injected kits and strength of each vial
- Total vials and nominal IU amount administered (calculated by eDiary)
- Reason for injection (e.g. planned injection, 1st injection for treatment of bleed, follow-up injections for treatment of bleed)
- If reason is bleeding, details regarding the bleeding (see Section 6.1.5.5)

The kit numbers, total vials, nominal IU per vial will be recorded, but not mapped to SDTM.

For each dose administration of rFVIIIFc, the variables Days in Study and Days in Period, will be derived as:

Date of Dose Administration – Start Date (of treatment and study period respectively) + 1 day

The number of exposure days will also be derived as number of days since study entry with rFVIIIFc administration up to and including the current administration.

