## PAREXEL International

### Statistical Analysis Plan

- The Baseline and the Week 2 Visit will be retained as is
- All other scheduled visits will be mapped to the closest even number of weeks, i.e. if a Visit takes place on Day 79 (with Day 1 being the day of treatment start), then it will be mapped to “ITI Period – Week 12”. In general, the week will be determined by calculating 2 times the rounded integer result of (Visit Date – Treatment Start)/14. If two visits will be mapped to the same even number of weeks, only the first one will be used in summary statistics.
- No summary statistics will be shown for unscheduled and optional visits (i.e. visit in Week 20 of tapering period if period is prolonged). In listings unscheduled visits will be shown with period, study day and study week (defined as study day/7 rounded up).

If not explicitly stated otherwise, the term “visit” will refer to nominal visit. The mapping of visits that took place outside of the allowed window visit, defined in the CSP, will be discussed in the DRM.

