## PAREXEL International

### Statistical Analysis Plan

Prognostic factors for ITI success will be summarized stratified by ITI outcome. Prognostic factors to consider include; historical peak inhibitor titer, pre-ITI inhibitor titer, factor VIII genotype, peak inhibitor titer on ITI, number of previous ITI attempts, time between inhibitor development and start of ITI. In this summary, patients will be included according the best ITI outcome they achieve (partial success is not also counted as failure and complete success is not also counted as partial success). The following categorical variables will be derived for this summary:

- Historical Peak Inhibitor Titer <200 BU (yes/no)
- Pre-ITI Inhibitor Titer <10 BU (yes/no)
- >5 Years between Diagnosis of Inhibitor and Start of ITI (yes/no)

The ITIFAS analysis set will be used for this analysis.

A figure will be presented showing the number and percentages of patients by ITI outcome versus time (up to Week 60, patients will be counted for each time point after their ITI outcome has been determined, regardless of discontinuation or relapse).

In addition, a treatment outcome listing will be produced, displaying for each patient:

- Outcome (ITI success, partial success, failure or not determinable [if withdrawal due to other reasons prior to 60 weeks])
- Study day each of the success criteria was met (blank if not met)
- Relapse (no or relapse criteria met)
- Days after ITI success to relapse

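### SAP 6.3.13.1 uses an ordinal week number as the time to ITI success, which overstates elapsed time by 1/7 to 1 week

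*SAP*

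**What the plan says.** SAP 6.3.13.1 analyses time to ITI success in weeks, by summary statistics and by Kaplan-Meier. It repeats the Kaplan-Meier analysis for confirmed negative titer and confirmed IR. The unit is set at the end of the section: "Week for the purpose of this analysis will be defined as follows: the study day/7, rounded up". An earlier sentence there describes weeks as consecutive blocks: "Each subsequent week then starts on the seventh day after the first day of the previous week". No first week is defined before that sentence.

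The day count is given elsewhere in the SAP. Section 6.1.2.2 derives days in study as "Date of Dose Administration – Start Date (of treatment and study period respectively) + 1 day". Section 6.3.1.1 works an example: "if a Visit takes place on Day 79 (with Day 1 being the day of treatment start"). Protocol 7.1.2 ties this to the visit schedule: "The first dose of rFVIIIFc will be administered at the baseline visit". Later visits are counted in whole weeks from baseline.

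SAP 6.3.1.1 has a second week rule, for time-based visits: "the week will be determined by calculating 2 times the rounded integer result of" the visit date minus treatment start, over 14. SAP 6.3.12.4 uses this mapping for the titer summary and the mean titer plot in the ITI period.

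**The concern.** A count that starts at 1 and is then taken up to the next whole number answers the question of which week of treatment the event fell in. It does not answer how long after first dose the event occurred, which is what a time-to-event analysis reports. Because the count starts at 1, the reported value is above the elapsed time on every day, so the error does not average out.

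Time to ITI success is the first-listed secondary endpoint, and the same variable serves the two component times. Two consequences would be visible in the report. A success exactly at the 60-week limit would be tabulated beyond it. And one target-day visit could carry one week number in the titer outputs and the next number in the time-to-criterion outputs.

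**Working it through.** **Inputs**
- Day 1 is the day of first dose, at baseline (SAP 6.1.2.2 and 6.3.1.1; Protocol 7.1.2).
- Visits fall a whole number of weeks *w* after baseline, so the target study day is 7*w* + 1.
- Windows are ±1 week for 4-weekly visits, and ±3 days for the Week 2 visit and the 2-weekly visits (Protocol Table 1).
- Success must be reached within 60 weeks (Protocol 7.1.2; SAP 6.1.5.3).

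**Formulas**, for study day *D*
- Elapsed weeks: E = (D − 1)/7
- SAP 6.3.13.1 week: W = D/7, taken up to the next whole number
- SAP 6.3.1.1 time-based visit: V = 2 × round((D − 1)/14)

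**The SAP's own example.** For Day 79, V = 2 × round(78/14) = 2 × round(5.57) = 12. This matches the SAP's Week 12 and confirms the Day 1 convention. On the same day W = 79/7 = 11.29, taken up to 12, and E = 78/7 = 11.14. The two SAP rules agree here, and W exceeds elapsed time by 0.86 week.

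**Visits on their target day**

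| Weeks after first dose | Study day | W (6.3.13.1) | V (6.3.1.1) | E |
|---|---|---|---|---|
| 2 | 15 | 3 | 2 | 2.0 |
| 4 | 29 | 5 | 4 | 4.0 |
| 12 | 85 | 13 | 12 | 12.0 |
| 36 | 253 | 37 | 36 | 36.0 |
| 60 | 421 | 61 | 60 | 60.0 |

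W = *w* + 1 for every *w* from 1 to 60.

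**All days.** Write D − 1 = 7q + r, with r from 0 to 6. Then W = q + 1 and E = q + r/7, so W − E = 1 − r/7. The excess is 1 week at r = 0, falls to 1/7 week at r = 6, and is never zero. Its mean over the seven values is (1 + 2 + … + 7)/49 = 28/49 = 4/7 week. Days 2 to 421 give the same minimum, maximum and mean.

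**Visits inside the window but off the target day**
- ±3 days: of 7 possible days, the 3 early ones get W = *w*; the other 4 get *w* + 1.
- ±1 week: of 15 possible days, the 7 early ones get *w*, 7 get *w* + 1, and the last gets *w* + 2.

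**The 60-week boundary.** Day 420: 420/7 = 60, reported as 60. Day 421: 421/7 = 60.14, reported as 61, although E = 60.0. Among days with E at or below 60, only Day 421 is reported as 61.

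**Relative size of a one-week excess.** 1/12 = 8.3% at 12 weeks; 1/60 = 1.7% at 60 weeks.

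**The case against.** *The rule is a recognised ordinal label and is prespecified.* The sentence on consecutive weeks in 6.3.13.1 describes weeks as blocks, and 6.3.1.1 uses the same day-to-week conversion to label unscheduled visits in listings. As a label it is sound. That does not make it a duration. Where the SAP measures durations elsewhere, it subtracts dates: time to relapse in 6.1.5.4 and duration of exposure in 6.3.14.

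*The time-based visit rule is not a gold standard.* It rounds to the nearest even week and exists to bin visits. It can itself be up to a week off, and both rules give 12 on Day 79. This stands: different rules for binning and for event time are not in themselves a contradiction. The point rests on the comparison with elapsed time; the mismatch with the titer outputs is a side effect.

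*The effect is minor.* This largely stands. The SAP plans no tests or confidence intervals (6.3.3), visits are 2 to 4 weeks apart, and 6.3.13.1 expects that the Kaplan-Meier median may not be estimable. The outcome listing in 6.3.12.1 gives the study day on which each criterion was met, so elapsed time can be recovered. Protocol 5.1.2 quotes earlier times in weeks, but the documents do not say how those studies counted weeks, so no bias in that comparison can be quantified.

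*Two stronger readings are tempting.* A reader might infer that every on-schedule visit is reported a week late. The visit windows contradict this: an early in-window visit keeps the number *w*. A reader might also infer that outcomes assigned at the end of 60 weeks drop out of Figure 14.2.1.4, which stops at Week 60 and of which 6.3.12.1 says "patients will be counted for each time point after their ITI outcome has been determined". The documents do not support that. The week rule in 6.3.13.1 is limited to its own analysis, and 6.3.12.1 states no week rule for the figure.

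**Conclusion.** The point holds as a small, systematic overstatement in the times to ITI success, confirmed negative titer and confirmed IR. An ordinal week stands in for a duration. The excess is at most one week, exactly one week on target days, and always upward. A Day 421 success would appear at week 61.

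A reader might take that last result to mean that patients lose their success classification. The documents do not support this: SAP 6.1.5.3 classifies on the criteria and the 60-week limit and does not use this week variable. The classification would be at risk only if the limit were programmed on that variable.

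The conclusion rests on three assumptions: study day in 6.3.13.1 counts as it does in 6.1.2.2 and 6.3.1.1; within 60 weeks means up to 420 days after first dose, that is, through Day 421; and the mean of 4/7 week gives each day equal weight. In practice visits cluster around target days, so the mean in the data may differ, but it stays between 1/7 and 1 week.

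The change is worth making because it alters reported numbers on a named secondary endpoint at almost no cost.

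**What to change.** In SAP 6.3.13.1, replace the week definition with: time in weeks = (event or censoring date − date of first dose)/7, unrounded. Apply it to the descriptive and Kaplan-Meier analyses of time to ITI success, confirmed negative titer and confirmed IR, with events and censored times treated alike. Delete the sentence on where each subsequent week starts, which has no antecedent and is no longer needed. The ordinal study week can stay in 6.3.1.1 as a listing label.

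A target-day visit then gives exactly *w*: Day 85 gives 12.0 in place of 13, and Day 421 gives 60.0 in place of 61. These agree with the time-based visit mapping on target days.

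The cost is one SAP sentence and one line of programming, with no new data. If the database is already locked, the SAP's introduction provides for recording the change in a SAP Addendum.
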